9.2 Setting

Within Denmark, Finland, and Sweden, we will include all individuals aged 65 years and above, and individuals below 65 years of age at high risk of adverse influenza outcomes, who are known residents. We will analyse each target group in separate cohorts in each country.

Eligibility criteria for study inclusion are:

- 1) Individuals 65+-years-of-age (trial 1)
- 2) Individuals in risk groups 18-64-yrs-of-age (trial 2)
- 3) Have a known residency within the specific country at start of study period

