9. RESEARCH METHODS

9.1 Study design

We will take advantage of the unique nationwide register-data available to us, and construct country-specific cohorts with individual-level information on dates of vaccination and dates of effectiveness endpoints together with relevant covariate information. All Nordic residents are assigned a unique personal identifier at birth or immigration, enabling linkage between register data. Nordic countries have universal and tax-financed healthcare systems and reporting to national registers is mandatory, providing near-complete follow-up of all residents over time.

The study period will start on 1st October 2024 in the three countries. This study start date corresponds to the start of the seasonal influenza vaccination program in the three countries. The study period will end on the last date of data availability at time of analyses during spring 2025.

The study design will build on our previous work with Covid-19 vaccination effectiveness in the Nordic countries (19,20). We will utilize a cohort design in a target trial emulation (TTE) framework to estimate both relative and absolute effects. The evaluations in 65+-yr-olds and risk groups 18-64-yr-olds will be designed as two separate target trial emulations. Key components of the specification and emulation of the pragmatic target trials of the effectiveness of brand-specific seasonal IVE using Nordic nationwide register data are included below in Table 1.

Table 1. Target trial emulation framework

Protocol	Target Trial Specification	Target Trial Emulation
Eligibility criteria	
 • Individuals 65+-years-of-age (trial 1) • Individuals in risk groups 18-64-yr-of-age (trial 2) • Have a permanent residency in Denmark, Finland, or Sweden at start of study period 	Same as for the target trials.
Treatment strategies	Vaccination with any of the following influenza vaccines InfluvacTetra, VaxigripTetra, FludTetra, FluarixTetra or Efluelda Tetra, October 1, 2024 to January 31, 2025 vs vaccination with placebo in the same period.	Same as for the target trials except vaccination with placebo is replaced by no vaccination with any of the vaccines under study.

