	Finland	The Finnish Population Information System. Recorded birth year. Age defined as 2024 minus birth year.	
	Sweden	The Total Population Register. Recorded birth year. Age defined as 2024 minus birth year.	
Sex	Denmark	The Civil Registration System. Defined as registered sex.	Binary: male, female
	Finland	The Finnish Population Information System. Defined as registered sex.	
	Sweden	The Total Population Register. Defined as registered sex.	
Region of residency	Denmark	The Civil Registration System. Defined by last known address at the start of the study period.	Categorical: Denmark, 5 levels; Finland, 5 levels; Sweden, 9 levels
	Finland	The Finnish Population Information System. Defined by last known municipality of residence.	

Variable	Country	Data source and details	Values/codes
	Sweden	The Total Population Register . Defined by last known address at the start of the study period.	
Comorbidity 1: Chronic pulmonary disease	Denmark	The National Patient Register . Defined as primary or secondary diagnoses registered prior to the start of the study period (look-back 7 years).	Binary: yes/no (ICD-10 codes: J40-J47, J60-J67, J684, J701, J703, J841, J920, J961, J982, J983)
	Finland	Care register for Health Care . Defined as primary or secondary diagnoses registered prior to the start of the study period (look-back 7 years).	Binary: yes/no (ICD-10 codes: J41-J44, J47)
	Sweden	National Patient Register . Defined as any recorded ICD-10 diagnosis during inpatient or outpatient contact and before first Covid-19 vaccination (look-back 7 years).	Binary: yes/no (ICD-10 codes: E84, J41-J47, J84, J98)
Comorbidity 2: Cardiovascular conditions	Denmark	The National Patient Register . Defined as primary or secondary diagnoses registered prior to the start of the study period (look-back 7 years).	Binary: yes/no (ICD-10 codes: I110, I20-I23, I420, I426-I429, I48, I500-I503, I508, I509, I60-I65)
	Finland	Care register for Health Care, Register of Primary Health Care Visits, Special Reimbursement Register and Prescription Centre database . Defined as primary or secondary diagnoses prior to the start of the study period (look-back 7 years).	Binary: yes/no (ICD-10 codes: I11-I13, I15, I20-I25, I60-I65)

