9.4 Data sources

All data sources are nationwide registers in native format. All study investigators have access to their country-specific data and can link data between registers for the purpose of our study. Given the near real-time availability of the data source, our analyses will provide timely evidence. Denmark and Finland will have full data availability for all variables (with no missing data; all the exposures, outcomes, or covariates are either present or not) during the study period and as reporting to national registers is mandatory/structurally implemented, this provides complete follow-up of all residents over time. Currently, Sweden has limited access to nationwide influenza vaccination data but will be able to provide data from four regions in Sweden with a combined population of 1,220,00 individuals. These include Uppsala Region (405,000), Jönköping Region (370,000), Blekinge Region (160,000), and Värmland Region (285,000).

Table 7. Overview of individual-level data sources in the three Nordic countries

Country	Data sources						
Denmark							
Title	Info	Type	Setting	Study availability	Update	Lag	Ref
The Danish Civil Registration System	The register provides the unique personal identifier for all permanent residents of Denmark that allows linkage between all Danish health care registers and civil registrations systems. In addition, it holds general demographic information such as birthdate and sex as well as continuously updated information and dates on historical addresses, immigration and emigration status, and death.	Register	Nationwide	1968- today	Daily	No lag	(24)

The Danish vaccination register	The register holds information on all vaccinations given in Denmark including information on vaccination date, brand, type, dose, and product batch number ever since November 15, 2015 (when reporting to the register became mandatory).	Register	Nationwide	2020 – today	Daily	No lag	(25)
The National patient registry	The register covers all hospital contacts/visits in Denmark with information on the duration of the contact/visit, department of admission and other hospital characteristics. Treating physician-assigned diagnoses have been registered according to ICD-10 codes since 1995.	Register	Nationwide	1995 - today	Daily	No lag	(26)

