There are no missing data in this study. All the exposures, outcomes or covariates are either present or not.

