9.5 Study size

Below we describe key target group sizes, vaccination coverage and recorded influenza infection incidences in the three Nordic countries for the 2023-2024 season. This provides a good indication of the possible study size for the 2024-2025 season. We expect to include at least 3.2 million individuals who are included in the key target groups for seasonal influenza vaccination across the 3 Nordic countries.

In Denmark, the total population of individuals aged 65 years and older, along with the population at increased risk below 65 years of age, consisted of 1,211 million and 554,780 individuals, respectively, as of 20 December 2024. (39) From 1 October 2024 to 20 December 2024, influenza vaccination coverage in these target groups was 75.6% and 29.2%, respectively. (39) As of 13 January 2025, there were 700 confirmed cases of influenza, including 414 hospitalisations, in older adults above 65 years. (40)

In Finland, the total population of individuals aged 65 years and older was 1,315 million with a vaccine coverage of 61% during the 2023-2024 season. The population at increased risk aged between 18 and 64 years comprised of 0,52 million individuals. The influenza A incidence was 65.5 per 10,000 person-years, and influenza A hospitalisation incidence was 5.4 per 100,000 person-years. As of 20 January 2025, there were 3224 confirmed cases of influenza in the Finnish population, including 81 hospitalisations due to influenza in adults aged 65 years and above. (41,42)

In Sweden, the total population of elderly 65 years and above in the four regions under study comprise of 280,000 individuals, with national influenza vaccination coverage of 69% in the 2023/2024 season. (43)

We will utilize all available data to us from the countries' nationwide registers (Denmark and Finland), and regional data sources (Sweden). The statistical power of our proposed study will be reflected in the 95% CI of the effectiveness estimates. We expect to have robust statistical precision for the most widely used influenza vaccine brands within the current season. (44,45)

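### Country-wide Swedish eligibility and nine undefined region levels contradict vaccination data that cover only four Swedish regions

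*Protocol*

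**What the plan says.** **Eligibility.** Criterion 3 in 9.2 reads "Have a known residency within the specific country at start of study period". Table 1 in 9.1 asks for the same at country level: "Have a permanent residency in Denmark, Finland, or Sweden at start of study period". Its emulation column makes no change for Sweden.

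**Matching levels.** Section 9.3 specifies exact matching on region of residence, among other variables. Table 6 defines the region variable as "Categorical: Denmark, 5 levels; Finland, 5 levels; Sweden, 9 levels". The nine Swedish levels are not named.

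**Exposure data.** Section 9.4 says that Sweden "will be able to provide data from four regions in Sweden with a combined population of 1,220,00 individuals" (the total has lost a zero). The regions are Uppsala, Jönköping, Blekinge and Värmland. Table 7 dates the national Swedish vaccination register from 2026 onwards, while the Swedish patient, prescription and communicable-disease registers are listed as nationwide.

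**Study size and limitations.** Section 9.5 says "the total population of elderly 65 years and above in the four regions under study comprise of 280,000 individuals". Section 9.9 lists the regional vaccination data as a limitation and expects most of the study population to come from Denmark and Finland.

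**Unobserved exposure.** The missing-data paragraph in 9.4 states that nothing is missing: "All the exposures, outcomes or covariates are either present or not". Section 9.3 treats as unvaccinated anyone who has not yet had a first dose this season. No rule covers residents whose vaccination cannot be observed.

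**The concern.** The eligibility and matching text describes a national Swedish cohort, but the exposure data support a four-region one. Because the outcome and covariate registers are nationwide, a 70-year-old outside the four regions meets every written criterion and has usable outcomes and comorbidities. Only the vaccination record is absent, and under a present-or-not reading that person stays unvaccinated throughout.

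Such people can enter the analyses in two ways, with opposite effects:

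- **Matched cohort.** A hidden vaccinee used as a control lowers the control risk and pulls Swedish VE towards zero. Such a control is also never censored at vaccination.
- **Fuzzy regression discontinuity analysis (9.8).** This compares ages 60-64 with 65-69. It is not matched on region and, unlike the test-negative design, is not limited to Denmark. Hidden vaccinations reduce the recorded jump in uptake at 65.

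Country-specific estimates are a planned output. Table 3 lists InfluvacTetra only for Denmark (risk groups and ages 65-69) and Sweden (including everyone above 65), so Swedish data matter more for that brand at older ages than the Swedish headcount suggests.

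**Working it through.** **1. The plan's own figure.** The four regional populations in 9.4 sum to 405,000 + 370,000 + 160,000 + 285,000 = 1,220,000, which confirms the intended total. The 280,000 aged 65 and over in 9.5 is 280/1,220 = 23% of that. At the 69% national coverage in 9.5, about 193,200 would be vaccinated and 86,800 unvaccinated.

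**2. Four regions against nine levels.** If each level is a single region, four regions cannot fill nine levels. Nine levels can apply to a four-region population only if they are subdivisions of those regions or national groupings of which some stay empty. The protocol does not say which.

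**3. When the matched cohort is biased.** Every recorded Swedish vaccinee lives in, or is recorded by, one of the four regions. With exact matching on region, a resident elsewhere becomes a control only if a level contains both covered and uncovered areas. If every level that contains covered residents lies wholly inside the covered regions, f = 0.

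**4. Size if f is above 0.** Let c be the share of hidden controls who are in fact vaccinated, taken as 0.69, and let VE be the true effect. Then

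observed VE = 1 − (1 − VE) / (1 − f × c × VE).

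For an assumed VE of 40% and f = 0.5: 1 − 0.60 / (1 − 0.5 × 0.69 × 0.40) = 1 − 0.60/0.862 = 30.4%.

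| True VE | f = 0 | f = 0.25 | f = 0.5 | f = 1 |
|---|---|---|---|---|
| 24% (Stockholm figure in section 7) | 24.0% | 20.7% | 17.1% | 8.9% |
| 40% (assumed) | 40.0% | 35.6% | 30.4% | 17.1% |
| 47% (pooled figure in section 7) | 47.0% | 42.3% | 36.7% | 21.6% |

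**5. How f could arise.** Take a level with equal covered and uncovered populations. Before vaccination starts, half of the apparently unvaccinated pool is uncovered (f = 0.5). Once the covered half reaches 69%, the share is 1/(1 + 0.31) = 0.76, and a true 40% would read 24%. Matching takes place on each vaccination day, so f would lie between these values in such a level. Since c is below 0.69 early in the season, the table shows the upper end of the dilution for each f.

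**6. Regression discontinuity.** The fuzzy estimate is the outcome jump divided by the uptake jump. If a share s of the Swedish 60-69-year-olds has no visible vaccination and the true jumps are equal everywhere, the recorded uptake jump is (1 − s) times the true one, while the outcome jump is unchanged. The estimate is multiplied by 1/(1 − s): 1.33 at an assumed s = 0.25 and 2 at s = 0.5. The protocol gives no figure for s.

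**7. Sweden's share.** The target groups listed in 9.5 sum to 1.211 + 0.555 + 1.315 + 0.52 + 0.28 = 3.88 million, of which the Swedish 280,000 is 7%. This is a share of heads, not the Swedish weight in the random-effects pooling.

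**The case against.** The strongest reply is that the intent is clear. Section 9.5 sizes Sweden on the four regions and contrasts national registers in Denmark and Finland with regional sources in Sweden. The expectation in 9.9 that most participants are Danish or Finnish makes best sense if other Swedes are outside the study. Exact matching on region may by itself remove every uncovered resident. The present-or-not statement first appears in 9.4 with reference to Denmark and Finland, and being unvaccinated is defined by not having had a dose, not by lacking a record. Finally, the quality control in 9.8 compares vaccination prevalence with national surveillance, so counting the rest of Sweden as unvaccinated should show.

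Most of this stands. A reader might infer that residents elsewhere will be counted as unvaccinated and that Swedish VE, and with it the pooled estimate, is diluted for every outcome and brand. The documents do not support that: f is unknown and may be 0, no pooled effect can be calculated, and in the regression discontinuity analysis the direction is the reverse.

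The reply does not remove the contradiction. The intent appears under sample size and limitations, whereas the operative rules in 9.2, Table 1 and Table 6 say something else. The missing-data paragraph repeats the present-or-not claim without limiting it to two countries. Matching protects only if the undefined levels allow it, and it does not protect the regression discontinuity analysis. A prevalence check can reveal a gross error but does not define the population.

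**Conclusion.** The concern holds as a contradiction between stated rules, with a conditional bias. Country-wide eligibility and nine undefined region levels cannot be reconciled with vaccination data from four regions.

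In the matched cohort, bias towards zero arises only if a matching level mixes covered and uncovered areas. For an assumed true VE of 40% and 69% coverage among hidden controls, the possible range runs from no bias (40% at f = 0) to an observed 17% at f = 1, an extreme that would need every Swedish control to come from outside the covered regions. In the regression discontinuity analysis, including uncovered Swedes would inflate the estimate and could make a real jump in uptake look weak. That analysis is supplementary, but it is meant for triangulation, and opposite errors in the two designs would mislead the comparison.

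Severity is moderate. Only Swedish and pooled results are exposed, the intended population can be read from 9.5 and 9.9, and the correction is simple. A further gap is that follow-up ends at emigration but not at a move out of the covered regions, so a control who moves and is then vaccinated is not censored. This is probably small, and the protocol gives no figure from which to size it.

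**What to change.** - **9.2 and Table 1:** for Sweden, require residence at study start in one of the four regions that supply vaccination data.
- **Table 6:** redefine the Swedish region levels so that each lies wholly within those regions, and name them.
- **9.8, regression discontinuity analysis:** state the same residence limit for any Swedish data. The prior event rate and negative control analyses reuse the main matched design and inherit it.
- **9.7 and Table 1 (minor):** censor the pair when either member moves out of the covered regions.
- **9.4:** limit the no-missing-data statement, for Swedish vaccination, to residents of the four regions, and correct the printed population total to 1,220,000.

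The cost is protocol wording and one residence filter in the Swedish data build. Table 6 already takes Swedish region from the address at study start. Censoring on a move also needs the dates of moves within Sweden. No planned size is lost, because 9.5 counts only the four regions, and no recorded vaccinee is lost beyond the few who live outside the region that recorded them. The change should be made before any effectiveness result is estimated.

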9.3 Variables

Exposures

The Nordic countries conduct annual influenza vaccination campaigns that focus on specific population groups at high risk of severe outcomes from influenza. These groups generally include the elderly, individuals with chronic health conditions, pregnant women, children and healthcare workers (Table 2).

The vaccines are provided free of charge and are typically administered before the peak flu season. In Denmark, vaccines for season 2024/2025 are administered from October 1st, in Finland from September 30th and in Sweden from October 15th. In immunization programmes across the three Nordic countries, the most frequently used quadrivalent inactivated influenza vaccine brands have been InfluvacTetra, VaxigripTetra, FluadTetra, FluarixTetra, and Efluelda Tetra, which are formulated

according to WHO's recommendations. The vaccines contain both seasonal influenza A subtypes, A(H3N2) and A(H1N1) pdm09, and both influenza B lineages, B/Victoria and B/Yamagata. Overview of the country-specific vaccine brands, types and target populations is provided in Table 3. At vaccination at general practitioners, regional vaccination centres or workplaces, individuals are vaccinated with the influenza vaccine available at the location.

An individual is defined as vaccinated starting from and including the day of the first influenza vaccination during the ongoing season, and as unvaccinated if they have yet to receive a first vaccine in the ongoing season.

Table 2. Influenza Vaccination Recommendations in Nordic Countries for season 2024/2025

Country	Target Groups for Influenza Vaccination
Denmark (21)	
 - Individuals over 65 - Persons with certain chronic diseases, including: 
 o Persons with chronic lung diseases o Persons with cardiovascular diseases (excluding isolated, well-regulated high blood pressure) o Persons with type 1 or type 2 diabetes o Persons with congenital or acquired immunodeficiency¹ o Persons with impaired respiration due to reduced muscle strength o Persons with chronic liver or kidney disease o Persons with other chronic diseases where the condition, according to the doctor's assessment, leads to an increased risk from Covid-19 or infection² - Persons with severe obesity (BMI > 35) - Persons with other serious diseases or conditions, where the condition, according to the doctor's assessment, poses a serious health risk from Covid-19 or influenza³ - Persons in the same household as individuals with congenital or acquired immunodeficiency, or children at increased risk of severe outcomes from Covid-19 or influenza - Pregnant women in the 2nd or 3rd trimester⁴ - Early retirees
Sweden (22)	
 - Persons 65 years and above, pregnant women, and persons with certain underlying diseases including: 
 o Persons with chronic lung diseases o Persons with cardiovascular diseases (excluding isolated, well-regulated high blood pressure)

	
 ○ Persons with type 1 or type 2 diabetes ○ Persons with congenital or acquired immunodeficiency¹ ○ Persons with impaired respiration due to reduced muscle strength ○ Persons with chronic liver or kidney disease ○ Persons with other chronic diseases where the condition, according to the doctor's assessment, leads to an increased risk from Covid-19 or infection² - Persons with severe obesity (BMI > 35) - Persons with other serious diseases or conditions, where the condition, according to the doctor's assessment, poses a serious health risk from Covid-19 or influenza³ - Persons in the same household as individuals with congenital or acquired immunodeficiency, or children at increased risk of severe outcomes from Covid-19 or influenza - Pregnant women in the 2nd or 3rd trimester⁴ - Health care workers
Finland (23)	
 - Pregnant women - Individuals aged 65 years or more - Children aged under 7 years - Individuals at risk because of illness or treatment 
 ○ Chronic heart disease ○ Chronic lung disease ○ Chronic metabolic disease ○ Chronic liver disease ○ Chronic kidney disease ○ Immunocompromising conditions due to disease or treatment ○ Down syndrome ○ A neurological disease affecting breathing ○ Psychotic disease ○ Obesity (body mass index > 40) ○ Other condition causing susceptibility for severe influenza - Those close to a person susceptible to serious influenza - Social welfare, healthcare and medical care personnel - Men starting their military service and women starting their voluntary military service

¹For example, persons with immunoglobulin deficiencies, organ or stem cell transplantation, cancer undergoing chemotherapy, or persons undergoing other immunosuppressive treatment.

² For example, persons with severe rheumatological disease, severe neurological disease, or short bowel syndrome.

³ For example, persons with severe mental illness, Down syndrome, or severe substance abuse.

⁴ Pregnant women with other risk factors for a severe course of influenza are recommended to receive the influenza vaccine starting from the first trimester.

Table 3: Overview of vaccine brands used in the national programmes in the Nordic countries in season 2024/2025

Country	Vaccine Brand	Vaccine Type	Target population
Denmark	InfluvacTetra®	QIV, surface antigen	Risk groups above 6 months Individuals 65-69 years
	Vaxigrip Tetra®	QIV, split virion	Risk groups above 6 months Individuals 65-69 years
	Efluelda Tetra®	QIV, adjuvanted (high-dose)	Clinical trial, 65+
	Fluad Tetra®	QIV, adjuvanted	Elderly 70+
	Flucelvax Tetra®	QIV, surface antigen, cell-based	Individuals with serious allergy to egg, neomycin or gentamycin
Finland	Vaxigrip Tetra®	QIV, split virion	All target groups (incl. 2-6-year-olds)
	Fluenz®	Attenuated live virus, nose spray	Children 2-6 years
	Fluad Tetra®	QIV, adjuvanted	Elderly ≥85y Severely immunocompromised ≥50y
	Efluelda Tetra®	QIV, adjuvanted (high-dose)	Outside national vaccination program
Sweden	Vaxigrip Tetra®	QIV, split virion	All target groups (risk groups above 6 months and all above 65)
	InfluvacTetra®	QIV, surface antigen	All target groups (risk groups above 6 months and all above 65)
	Efluelda Tetra®	QIV, adjuvanted (high-dose)	Individuals in long term care facilities (nursery homes for elderly) only

Outcomes

We will estimate VE against the laboratory-confirmed influenza outcomes listed below.

Table 4. Laboratory-confirmed influenza outcomes

Variable	Country	Data source and details
Laboratory-confirmed influenza A	Denmark	Danish Microbiology Database . Defined as a laboratory-confirmed positive influenza test with a known subtype of influenza A.
	Finland	National Infectious Diseases Register . Defined as a laboratory-confirmed positive influenza test with a known subtype of influenza A.

	Sweden	Register on surveillance of notifiable communicable diseases (SmiNet). Defined as a laboratory-confirmed positive influenza test with a known subtype of influenza A.
Laboratory-confirmed influenza B	Denmark	Danish Microbiology Database. Defined as a laboratory-confirmed positive influenza B test result.
	Finland	National Infectious Diseases Register. Defined as a laboratory-confirmed positive influenza B test result.
	Sweden	Register on surveillance of notifiable communicable diseases (SmiNet). Defined as a laboratory-confirmed positive influenza B test result.
Hospitalisation due to influenza	Denmark	The National Patient Register and the Danish Microbiology Database. Defined as a hospitalization with a PCR positive test for influenza within 14 days before to 2 days after the admission date, b) inpatient contact or at least 12 hours of contact, and c) influenza-like illness relevant diagnosis code (ICD-10: J09, J10, J11)
	Finland	National Care Register for Health Care and the National Infectious Diseases Register. Defined as a hospitalization with a PCR positive test for influenza within 14 days before to 2 days after the admission date, b) inpatient contact, and c) influenza-like illness relevant diagnosis code (ICD-10: J09, J10, J11)
	Sweden	The Swedish Patient Register and the Register on surveillance of notifiable communicable diseases (SmiNet). Defined as a hospitalization with a PCR positive test for influenza within 14 days before to 2 days after the admission date, b) inpatient contact or at least 12 hours of contact, and c) influenza-like illness relevant diagnosis code (ICD-10: J09, J10, J11)
Influenza-related death	Denmark	The Civil Registration System and the Danish Microbiology Database. Defined as (the date of) death within 30 days after PCR positive test for influenza.
	Finland	The Finnish Population Information System and the National Infectious Diseases Register. Defined as (the date of) death within 30 days after PCR positive test for influenza.
	Sweden	The Total Population Register, the Cause of Death Register, and the Swedish Patient Register and the Register on surveillance of notifiable communicable diseases (SmiNet). Defined as (the date of) death within 30 days after PCR positive test for influenza.

Furthermore, medically attended outcomes presented in Table 5 will be assessed.

Table 5. Medically attended influenza outcomes

Variable	Country	Data source and details
Influenza-like-illness	Denmark	The National Patient Register. Defined as ICD-10 diagnostic codes J09, J10 and J11 used as a primary or secondary diagnosis.
	Finland	National Care Register for Health Care. Defined as ICD-10 diagnostic codes J09, J10 and J11 used as a primary diagnosis.
	Sweden	The Swedish Patient Register. Defined as ICD-10 diagnostic codes J09, J10 and J11 used as a primary diagnosis.
Hospitalisation for acute respiratory infections (ARI) and severe acute respiratory infections (SARI)	Denmark	The National Patient Register. A hospitalised patient is a SARI patient who a) has been admitted to hospital during the study period and has not been discharged to their home or home equivalent, b) inpatient contact or at least 12 hours of contact, and c) a ARI/SARI relevant primary diagnosis code (ICD-10: J09-J22).
	Finland	National Care Register for Health Care and the National Infectious Diseases Register. A hospitalised patient is a SARI patient who a) has been admitted to hospital during the study period and has not been discharged to their home or home equivalent, b) inpatient contact or at least 12 hours of contact, and c) a ARI/SARI relevant primary diagnosis code (ICD-10: J09-J22)
	Sweden	The Swedish Patient Register and the Register on surveillance of notifiable communicable diseases (SmiNet). A hospitalised patient is a SARI patient who a) has been admitted to hospital during the study period and has not been discharged to their home or home equivalent, b) inpatient contact or at least 12 hours of contact, and c) a ARI/SARI relevant primary diagnosis code (ICD-10: J09-J22)
ICU admission	Denmark	The National Patient Register and the Danish Microbiology Database. Defined as admission to an intensive care unit facility during hospitalization for influenza.
	Finland	Finnish Intensive Care Consortium's Quality Register for Intensive Care, National Care Register for Health Care and the National Infectious Diseases Register. Defined as admission to an intensive care unit facility during hospitalization for influenza.
	Sweden	The Swedish Patient Register, Quality Register for Intensive Care and the Register on surveillance of notifiable communicable diseases (SmiNet). Defined as admission to an intensive care unit facility during hospitalization for influenza.
All-cause mortality	Denmark	The Civil Registration Defined as a recording of death in the respective administrative demographic register (vital status is prospectively updated in these registers and also include information on the date of death).
	Finland	The Finnish Population Information System

		Defined as a recording of death in the respective administrative demographic register (vital status is prospectively updated in these registers and also include information on the date of death).
	Sweden	The Total Population Register, the Cause of Death Register Defined as a recording of death in the respective administrative demographic register (vital status is prospectively updated in these registers and also include information on the date of death).

Covariates

Determinants of vaccination and study outcomes are potential confounders in our studies. The richness of our health registers will allow us to provide detailed characterisations of health and disease status in individuals. We will be able to take the following confounders into account through exact matching: age (5-yr bins), sex, region of residency, and number of selected comorbidities (by 0, 1, 2, or ≥ 3 of chronic pulmonary disease, cardiovascular conditions, diabetes, autoimmunity-related conditions, cancer, and moderate-to-severe renal disease) as presented in Table 6.

Table 6. List of covariates

Variable	Country	Data source and details	Values/codes
Age	Denmark	The Civil Registration System. Recorded birth year. Age defined as 2024 minus birth year.	Categorical (for adjustment, using birth year): 5-year bins Binary (for stratification): $</\geq 75$ years
	Finland	The Finnish Population Information System. Recorded birth year. Age defined as 2024 minus birth year.	
	Sweden	The Total Population Register. Recorded birth year. Age defined as 2024 minus birth year.	
Sex	Denmark	The Civil Registration System. Defined as registered sex.	Binary: male, female
	Finland	The Finnish Population Information System. Defined as registered sex.	
	Sweden	The Total Population Register. Defined as registered sex.	
Region of residency	Denmark	The Civil Registration System. Defined by last known address at the start of the study period.	Categorical: Denmark, 5 levels; Finland, 5 levels; Sweden, 9 levels
	Finland	The Finnish Population Information System. Defined by last known municipality of residence.	

Variable	Country	Data source and details	Values/codes
	Sweden	The Total Population Register . Defined by last known address at the start of the study period.	
Comorbidity 1: Chronic pulmonary disease	Denmark	The National Patient Register . Defined as primary or secondary diagnoses registered prior to the start of the study period (look-back 7 years).	Binary: yes/no (ICD-10 codes: J40-J47, J60-J67, J684, J701, J703, J841, J920, J961, J982, J983)
	Finland	Care register for Health Care . Defined as primary or secondary diagnoses registered prior to the start of the study period (look-back 7 years).	Binary: yes/no (ICD-10 codes: J41-J44, J47)
	Sweden	National Patient Register . Defined as any recorded ICD-10 diagnosis during inpatient or outpatient contact and before first Covid-19 vaccination (look-back 7 years).	Binary: yes/no (ICD-10 codes: E84, J41-J47, J84, J98)
Comorbidity 2: Cardiovascular conditions	Denmark	The National Patient Register . Defined as primary or secondary diagnoses registered prior to the start of the study period (look-back 7 years).	Binary: yes/no (ICD-10 codes: I110, I20-I23, I420, I426-I429, I48, I500-I503, I508, I509, I60-I65)
	Finland	Care register for Health Care, Register of Primary Health Care Visits, Special Reimbursement Register and Prescription Centre database . Defined as primary or secondary diagnoses prior to the start of the study period (look-back 7 years).	Binary: yes/no (ICD-10 codes: I11-I13, I15, I20-I25, I60-I65)
	Sweden	National Patient Register . Defined as any recorded ICD-10 diagnosis during inpatient or outpatient contact prior to the start of the study period (look-back 7 years).	Binary: yes/no (ICD-10 codes: I05-I09, I110, I20-I28, I34-I37, I39, I42, I43, I46, I48-I50, I60-I65)
Comorbidity 3: Diabetes	Denmark	The National Patient Register . Defined as primary or secondary diagnoses registered prior to the start of the study period (look-back 7 years).	Binary: yes/no (ICD-10 codes: E10-E11)
	Finland	Care register for Health Care, Register of Primary Health Care Visits, Special Reimbursement Register and Prescription Centre database . Defined as primary or secondary diagnoses prior to the start of the study period or drug prescriptions (look-back 7 years).	Binary: yes/no (ICD-10 codes: E10, E11, E13-E14; ICPC-2 codes: T89, T90; ATC codes: A10A, A10B)
	Sweden	National Patient Register . Defined as any recorded ICD-10 diagnosis during inpatient or outpatient contact prior to the start of the study period (look-back 7 years). Swedish Prescribed Drug Register . Antidiabetic drugs use defined as ≥ 2 filled prescriptions during 2020.	Binary: yes/no (ICD-10 codes: E10-E14; ATC code: A10)
Comorbidity 4: Autoimmunity-related conditions ^a	Denmark	The National Patient Register . Defined as primary or secondary diagnoses registered prior to the start of the study period (look-back 7 years).	Binary: yes/no (ICD-10 codes: D510, D590, D591, D690, D693, D86, E050, E063, E271, E272, G122G, G35, G610, G700, I00, I01, K50, K51, K743, K900, L12, L40, L52, L80, L93, M05, M06, M08,

Variable	Country	Data source and details	Values/codes
			M300, M313, M315, M316, M32, M33, M34, M35, M45)
	Finland	Care register for Health Care, Special Reimbursement Register and Prescription Centre database. Defined as primary or secondary diagnoses prior to the start of the follow-up or drug prescriptions (look-back 7 years).	Binary: yes/no (ICD-10 codes: D7081, D7089, D80–D84, E250, E271, E272, E274, E310, E896, D86, K50, K51, L40, M02, M05–M07, M139, M45, M460, M461, M469, M941; ATC-codes: H02AB02, H02AB04, H02AB06, H02AB07, L01BA01, L01XC02, L04AA06, L04AA10, L04AA13, L04AA18, L04AA24, L04AA26, L04AA29, L04AA33, L04AA37, L04AB, L04AC, L04AD01, L04AD02, L04AX01, L04AX03)
	Sweden	National Patient Register. Defined as any recorded ICD-10 diagnosis during inpatient or outpatient contact prior to the start of the study period (look-back 7 years).	Binary: yes/no (ICD-10 codes: D86, G35, K50, K51, L40, M05–M09, M13, M14, M45)
Comorbidity 5: Cancer	Denmark	The National Patient Register. Defined as primary or secondary diagnoses registered prior to the start of the study period (look-back 7 years).	Binary: yes/no (ICD-10 codes: C00–C85 (without C44), C88, C90–C96)
	Finland	Care register for Health Care and Special Reimbursement Register. Defined as primary or secondary diagnoses registered within 7 years prior to the start of the study period.	Binary: yes/no (ICD-10 codes: C00–C43, C45–C80, C97, D05.1, D39)
	Sweden	National Patient Register. Defined as any recorded ICD-10 diagnosis during inpatient or outpatient contact prior to the start of the study period (look-back 7 years).	Binary: yes/no (ICD-10 codes: C00–C96 (without C44), D45–D47)
Comorbidity 6: Moderate to severe renal disease	Denmark	The National Patient Register. Defined as primary or secondary diagnoses registered prior to the start of the study period (look-back 7 years).	Binary: yes/no (ICD-10 codes: I12, I13, N00–N05, N07, N11, N14, N17–N19, Q61)
	Finland	Care register for Health Care. Defined as primary or secondary diagnoses prior to the start of the study period (look-back 7 years).	Binary: yes/no (ICD-10 codes: I12, I13, N00–N05, N07, N08, N11, N14, N18, N19, E102, E112, E142)
	Sweden	National Patient Register. Defined as any recorded ICD-10 diagnosis during inpatient or outpatient contact prior to the start of the study period (look-back 7 years).	Binary: yes/no (ICD-10 codes: I12, I13, N00–N05, N07, N11, N14, N17–N19, Q61)

^a Autoimmunity-related conditions includes a range disorders such as inflammatory bowel diseases, diseases involving the blood, immune mechanism or endocrine systems, inflammatory rheumatic diseases, psoriasis, lupus erythematosus, multiple sclerosis; subject to country-specific definitions. The selected diagnosis codes to define comorbidities were country-specific, based on inputs from national experts and country-specific registration practices as part of the general national surveillance purposes. This was done as we anticipated that country-specific definitions were likely better at identifying comorbidity-related risk groups within each country than a common set of code definitions.

We provide country specific estimates (by design) and will stratify according to:

- Influenza vaccine brand
- Age groups: individuals <65 years – stratified by 5-yr age bins, ≥65 years – stratified 65 – 75 years of age, and >75 years of age
- Sex

